## GLOSSARY OF ABBREVIATIONS

AE	adverse event
AESIs	adverse events of special interest
ALT	alanine aminotransferase
ANCOVA	analysis of covariance
aTNF	anti-tumor necrosis factor
AST	aspartate aminotransferase
CMH	Cochran-Mantel-Haenszel
CRP	C-reactive protein
CRF	Case Report Form
CS	corticosteroid
CSR	Clinical Study Report
ES	Endoscopic Subscore
FFPE	formalin-fixed paraffin-embedded
HS	Hybrid Sigmoid
IBD	inflammatory bowel disease
IBDQ	Inflammatory Bowel Disease Questionnaire
iDCC	independent Data Coordinating Center
iDMC	independent Data Monitoring Committee
IS	immunosuppressant
IxRS	interactive voice/web based response system
LoPO	list of planned outputs
MCS	Mayo Clinic Score
MedDRA	Medical Dictionary for Regulatory Activities
mITT	modified intent to treat
mMCS	modified Mayo Clinic Score
MMRM	mixed-model repeated measures
NHI	Nancy Histology Index
OLE	open label extension
OLI	open label induction
PD	pharmacodynamic
PGA	Physician's Global Assessment
PK	pharmacokinetic
pMCS	partial Mayo Clinic Score
RB	rectal bleeding
RHI	Robarts Histopathological Index
SAE	serious adverse event
SAP	Statistical Analysis Plan
SF	stool frequency
SMQ	standardized MedDRA query
TNF	tumor necrosis factor
UC	ulcerative colitis
UC-PRO/SS	Ulcerative Colitis Patient-Reported Outcome Signs and Symptoms
ULN	upper limit of normal

## **GLOSSARY OF ABBREVIATIONS**

WOCF Worse Observation Carried Forward

## 1. **BACKGROUND**

This etrolizumab project Statistical Analysis Plan (SAP) describes the study design and analyses that are common to the Phase III etrolizumab studies in ulcerative colitis (UC) patients detailed in [Table 1](#). Elements of the study design and analysis unique to the individual studies will be explained in the respective study SAPs.

**Table 1 Study Descriptions**

Study	Study Description
GA28948 (Hibiscus I) and GA28949 (Hibiscus II)	Two identical placebo-controlled induction studies assessing the efficacy and safety of etrolizumab compared to adalimumab and placebo in patients with moderate to severe active ulcerative colitis who are naive to TNF inhibitors
GA29102 (Laurel)	Placebo-controlled, maintenance study assessing the efficacy and safety of etrolizumab in patients with moderate to severe active ulcerative colitis who are naive to TNF inhibitors
GA29103 (Gardenia)	Head To Head study to evaluate the efficacy and safety of etrolizumab compared with Infliximab in patients with moderate to severe active ulcerative colitis who are naive to TNF inhibitors
GA28950 (Hickory)	Placebo-controlled, induction and maintenance study assessing the efficacy and safety of etrolizumab in patients with moderate to severe active ulcerative colitis who have been previously exposed to TNF inhibitors

TNF=tumor necrosis factor.

Studies GA28950 and GA29102 are made up of two phases: Induction Phase and Maintenance Phase. For the purpose of statistical analyses, the Induction and Maintenance Phases of Studies GA28950 and GA29102 will be treated as two independent studies and analyzed separately. Studies GA28948 and GA28949 are induction studies. Study GA29103 is a treat-through study design with no re-randomization into the Maintenance Phase; therefore, the Induction and Maintenance Phases will be analyzed as one study.

The analysis of data will be performed once all the data have been collected in the database for the primary analysis as described in the study SAPs.

## 2. **STUDY DESIGN**

### 2.1 **PROTOCOL SYNOPSIS**

For individual study Protocol Synopses and Schedules of Assessments, refer to the study SAP [Appendix 1](#) and [Appendix 2](#), respectively.

## **2.2 OUTCOME MEASURES**

For individual study outcome measures, refer to the study SAPs.

## **2.3 DETERMINATION OF SAMPLE SIZE**

For details of individual study sample size, refer to the study SAPs.

## **2.4 ANALYSIS TIMING**

For details of the analysis timing for individual studies, refer to the study SAPs.

## **3. STUDY CONDUCT**

### **3.1 RANDOMIZATION**

An independent interactive voice/Web-based response system (IxRS) vendor will conduct the randomization for all studies and the independent Data Coordinating Center (iDCC) will perform regular checks of the randomization scheme using unblinded data. The patient randomization list will be generated by the IxRS with use of a pre-defined randomization specification. During study conduct the randomization list will not be available to the study sites, study monitors, project statisticians, or the Sponsor's project team. The study team will remain blinded to study drug. If unblinding is necessary for patient management (in the case of a serious adverse event [SAE]), the investigator will be able to break the treatment code by contacting the IxRS. Treatment codes should not be broken except in emergency situations. If the investigator wishes to know the identity of the study drug for any other reason, he or she should contact the Medical Monitor. The investigator should document and provide an explanation for any premature unblinding (e.g., accidental unblinding, unblinding due to an SAE as per health authority reporting requirements). The Sponsor safety reporting department (independent to the study team) will unblind the identity of the study medication for all unexpected SAEs that are considered by the investigator to be related to study drug per safety reference document(s), such as the Investigator's Brochure, Core Data Sheet, and Summary of Product Characteristics (SmPC). Details of patients who are unblinded during the study will be included in the individual study Clinical Study Reports (CSRs).

After the end of randomization, the data entered into the IxRS system will be reconciled with the data entered into the clinical database. In particular, the kit assignments and stratification factors will be checked. Discrepancies between the IxRS and clinical database will be listed in the CSR and raised as protocol deviations. The statistical analyses will be conducted using IxRS stratification factors, and sensitivity analysis using clinical database data will be conducted if required.

Further details of stratification factors for each study is included in the study SAPs.

### **3.2 INDEPENDENT REVIEW FACILITY**

The efficacy measure Mayo Clinic Score (MCS) requires endoscopic subscores to be collected. Central reading of endoscopies will be performed throughout the studies by

an independent review facility. Data collected at sites as video clips are read centrally by an independent gastroenterologist experienced in inflammatory bowel disease (IBD). The independent reader will be blinded to the patient's clinical activity and treatment allocation. Reads are collected and read locally and then again centrally. The adjudication is carried out in two stages:

1. A second central reading is performed if the local and initial central reading do not agree or the initial central reading cannot be performed.
2. The local and central reading results are combined in a final Mayo Endoscopy subscore using the median among readers, rounded up to the nearest integer.

Further details are available in the Independent Review Charter.

The efficacy measure of histologic remission requires independent scoring. The histologic scoring will be performed by a small pool of central readers who are blinded both to treatment arm and timepoint. The scoring database will ensure that all slides for a given patient are scored by the same reader. Slide image scores are based on formalin-fixed paraffin-embedded (FFPE) biopsies from the most inflamed region of the sigmoid colon. Scores are queried for discrepancies between Nancy Histologic Index (NHI) and Geboes results (e.g., NHI < 4, indicating no erosions/ulcerations, and Geboes subgrades 5.3 or 5.4, indicating the presence of erosions/ulcerations). Queries may lead to the same reader reassessing the relevant slide images and revising the scores as they deem necessary. Further details are available in the Image Review Charter.

### **3.3 DATA MONITORING**

An independent Data Monitoring Committee (iDMC) will monitor safety and study conduct on an ongoing basis for all studies. The iDMC will meet approximately every 6 months. Further details are available in the iDMC Charter.

## **4. STATISTICAL METHODS**

### **4.1 ANALYSIS POPULATIONS**

Analysis populations are reported in the individual study SAPs.

### **4.2 ANALYSIS OF STUDY CONDUCT**

For details on the analysis of study conduct, refer to the individual study SAPs.

### **4.3 ANALYSIS OF TREATMENT GROUP COMPARABILITY**

To review treatment group comparability within each study a number of variables collected at baseline will be compared across treatment groups. Baseline is defined as the last available assessment prior to first receipt of study drug.

For continuous variables, descriptive statistics including n, mean, median, SD, minimum, and maximum will be calculated. For categorical variables, number and percentage in

each category will be displayed. The units/categories to be used are indicated within the brackets and separated by commas.

Summaries by treatment group will be presented for all analysis populations. Demographics and baseline characteristics presented for patients in the Maintenance Phases will use the data collected from their baseline visits.

#### **4.3.1 Demographics**

Demographics presented will include;

- Age at randomization (years), descriptive statistics, and number and percentage of patients in the following categories: 18–<40, ≥40–<65, ≥65
- Gender, number and percentage of patients in the following categories: male, female
- Race, number and percentage of patients in the following categories:
  - American Indian or Alaskan Native
  - Asian
  - Black or African American
  - Native Hawaiian or other Pacific Islander
  - White
  - Other (includes Other, Multiple, and Unknown)

For Listings the Race Category Other, multiple and unknown will be reported. For summaries and subgroups the combined category ‘Other’ will be used.

- Region, number and percentage of patients in the following categories:
  - Central /Eastern Europe
  - USA
  - Western/Northern Europe, Canada, Australia, New Zealand
  - Asia
  - Latin America
  - Other
- Ethnicity, number and percentage of patients in the following categories: Hispanic or Latino, Not Hispanic or Latino, Not reported, Unknown
- Body Weight (kg), descriptive statistics
- Body Mass Index (BMI; kg/m^2), descriptive statistics
- Tobacco Use, number and percentage of patients in the following categories: Never, Previous, Current

### **4.3.2 Baseline Disease Characteristics**

Details of efficacy parameters definitions listed below are provided in Section 4.4.2.

- Duration of disease (years), descriptive statistics, and number and percentage of patients in the following categories:  $<3$ ,  $\geq 3$ - $<8$ ,  $\geq 8$
- Disease extent, number and percentage of patients in the following categories: Left-sided colitis, Extensive colitis, Pancolitis
- Serum C-reactive protein (CRP) (mg/L), descriptive statistics, and number and percentage of patients in the following categories:  $\leq 2.87$ ,  $>2.87$ - $\leq 10$ ,  $>10$
- Fecal calprotectin ( $\mu\text{g/g}$ ), descriptive statistics including median, 25th and 75th percentiles and number and percentage of patients in the following categories:  $<250$ ,  $\geq 250$ - $<500$ ,  $\geq 500$
- Mayo Clinic Score (MCS), descriptive statistics, and number and percentage of patients in the following categories:  $\text{MCS} \leq 9$ ,  $\text{MCS} \geq 10$
- Partial Mayo Clinic Score (pMCS) –Descriptive statistics
- Modified Mayo Clinic Score (mMCS) –Descriptive statistics
- Modified Mayo Clinic Score (mMCS) (excluding friability from Mayo ES=1) – Descriptive statistics
- Stratification Factor MCS Score per IxRS, number and percentage of patients in each category:  $\text{MCS} \leq 9$ ,  $\text{MCS} \geq 10$
- Stool Frequency (SF) – Descriptive statistics.
- Rectal Bleeding (RB) – Descriptive statistics.
- Physician’s Global Assessment (PGA) – Descriptive statistics
- Endoscopy (ES) – Descriptive statistics.
- Ulcerative Colitis Patient-Reported Outcomes, Signs and Symptoms (UC-PRO/SS): Functional – Descriptive statistics
- UC-PRO/SS: Bowel – Descriptive statistics
- UC-PRO: Systemic Symptoms – Descriptive Statistics
- Inflammatory Bowel Disease Questionnaire (IBDQ) – Descriptive statistics
- Nancy Histological Index (NHI) – Descriptive statistics and frequencies (number and percentage per grade)
- Robarts Histopathological Index (RHI) – Descriptive statistics and frequencies (number and percentage per grade)
- Geboes Grading Scale Score – Descriptive statistics and frequencies (number and percentage per grade)

### **4.3.3 Baseline Disease Medications**

All data types are categorical and the number and percentage of patients will be presented for each category denoted in brackets.

- Corticosteroid (CS) use at baseline (yes, no)
- Stratification Factors (IxRS): Corticosteroid (CS) use at baseline (yes, no)
- Immunosuppressant (IS) use at baseline (yes, no)
- Stratification Factors (IxRS): Immunosuppressant (IS) use at baseline number (yes, no)
- Corticosteroid and Immunosuppressant categories (CS alone, IS alone, CS and IS, None)
- Prior anti-tumor necrosis factor (aTNF) medication (yes, no)
- Prior aTNF medication (1 failure,  $\geq 2$  failures, Refractory =Primary Non-response, Loss of response =Secondary Loss of Response, Intolerant, Unknown)

Prior aTNF use is only relevant for Study GA28950; all patients in other studies are aTNF-naive.

## **4.4 EFFICACY ANALYSIS**

The hierarchical priority of key secondary endpoints and analysis populations are available in the study SAPs. All formal statistical comparisons for binary data will use the Cochran-Mantel-Haenszel (CMH) test statistics stratified by the factors used at randomization as described in the study SAPs. For all analyses in both the Induction and Maintenance Phases where comparisons back to baseline are made, baseline is defined as the last available assessment prior to first receipt of study drug in the Induction Phase. For all analyses the point estimate, 95% CIs and p-value will be reported.

### **4.4.1 Efficacy Endpoints**

All primary endpoints for the studies are derived from the MCS. Further details of the individual primary endpoint evaluation and treatment effects (estimands) are provided in the study SAPs. All primary endpoints are categorical and formal statistical comparisons between the treatment arms will use the CMH test statistics stratified by the factors used at randomization. In addition, a selection of secondary endpoints across the studies evaluating remission, clinical remission and clinical response are also derived using the full MCS.

### **4.4.2 Endpoint Definitions**

This section provides endpoint definitions for endpoints common across studies. Further study specific details including analysis timepoints and populations will be included in the study SAPs.

#### **4.4.2.1 Mayo Clinic Score**

The MCS is a composite endpoint made up of four components. The score ranges from 0 to 12 with higher scores indicating more severe disease.

The MCS is used to determine a number of efficacy endpoints as described in [Table 3](#).

$$\text{MCS} = \text{Stool Frequency subscore} + \text{Rectal Bleeding subscore} + \text{Endoscopy subscore} + \text{PGA subscore}$$

##### **4.4.2.1.1 Stool Frequency and Rectal Bleeding**

Stool frequency (SF) and rectal bleeding (RB) data are collected daily via patient's diaries and each day a patient provides a score between 0-3 for each component.

##### **Stool Frequency Subscore 0–3**

- 0= Normal number of stools for this patient
- 1= 1 to 2 stools more than normal
- 2= 3 to 4 more stools than normal
- 3= 5 or more stools than normal

##### **Rectal Bleeding Subscore 0–3**

- 0= No blood in stool
  - 1= Streaks of blood with stool less than half the time
  - 2= Obvious blood with stool most of the time
  - 3= Blood alone passed
- Stool Frequency (SF) subscore= Average of 3 days daily diary scores
- Rectal Bleeding (RB) subscore= Worst value of 3 days daily diary scores

[Table 2](#) summarizes the different scenarios for calculating SF/RB sub score in the analyses. The three days of daily diary data used to calculate the subscores described above are selected from the days most recent to, (but not including) a pre specified date, and this is called the 'anchor date'.

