- The baseline stool frequency value will be taken from patient e-diary recordings that are entered between Day –22 (inclusive) and bowel preparation for the screening endoscopy and will be calculated as the average (rounded to the nearest integer) from the three most recent stool frequency scores that were entered just prior to the day of bowel preparation. However, up to three post-endoscopy scores, starting with the score recorded 2 days after the endoscopy, may be used to calculate baseline stool frequency, but ONLY when fewer than three scores are available between Day –22 and bowel preparation (see [Figure 1](#) below). The days selected for this calculation are intended to prevent the use of stool frequency recordings during the screening period that are impacted by bowel preparation and endoscopy, including the day immediately following the endoscopy.

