Appendix 4 Mayo Clinic Score Measurement (cont.)

- The post-baseline stool frequency value for endpoint assessment will be calculated as the average (rounded to the nearest integer) from the three most recent stool frequency scores that were entered in the e-diary within the 7 days prior to the clinic visit and prior to the days devoted to bowel preparation and endoscopy.

2. Rectal bleeding

- Rectal bleeding is to be recorded daily from screening to the end of the study in the e-diary
- The rectal bleeding score is to be categorized from 0–3 according to the definition given in 2 above
- Patients are to be instructed to ignore any blood which is caused by menstruation or hemorrhoids
- The baseline value for the rectal bleeding score will be taken from patient e-diary recordings that are entered between Day –22 (inclusive) and bowel preparation for the screening endoscopy and will be determined by the worst recording from the three most recent scores that were entered just prior to the day of bowel preparation. However, up to three post-endoscopy scores, starting with the score recorded 2 days after the endoscopy, may be used to calculate baseline rectal bleeding, but ONLY when fewer than three scores are available between Day –22 and bowel preparation (see [Figure 1](#) below). The days selected for this calculation are intended to prevent the use of rectal bleeding recordings during the screening period that are impacted by bowel preparation and endoscopy, including the day immediately following the endoscopy.
- The post-baseline rectal bleeding value for endpoint assessment will be determined by the worst of the three most recent rectal bleeding scores that were entered in the e-diary within the 7 days prior to the clinic visit and prior to the days devoted to bowel preparation and endoscopy.

3. Endoscopy Subscore

This score is provided by the endoscopy reading vendor as a subscore of 0 to 3.

- Findings on endoscopy will be documented by photographic evidence (central reading of endoscopy videos)
- The score will be based upon the worst affected segment (if mucosal appearance varies) *for study conduct, except at post-baseline time points, when the sigmoid colon MCS endoscopic subscore will be used if the baseline sigmoid colon MCS endoscopic subscore is 2–3.*

Note: The time window for performing endoscopy during the screening is 4–16 days prior to Day 1 (i.e., Day –16 to Day –4).

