### **3. STUDY CONDUCT**

#### **3.1 RANDOMIZATION**

Details of the randomization process are included in the project SAP, Section 3.1. The statistical analyses will be conducted using the stratification factors entered into the interactive voice/web based response system (IxRS) system at randomization. Sensitivity analysis of the primary endpoints using data collected in the clinical database will be conducted as required, if the database does not match IxRS due to incorrect stratification data being collected in IxRS at randomization. Due to low or zero counts in any one stratum, the stratification factors may need to be combined or removed in the primary analysis to ensure the Cochran–Mantel–Haenszel (CMH) test is not invalidated. This approach has been applied to the Maintenance Phase as described in Section 3.1.1, however further combining or removal may be required to ensure the analysis is not invalidated due to zero counts.

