**Proportion of patients in remission at Week 62 among clinical responders at Week 10**

$$= \frac{\text{\# of patients in remission at Week 62}}{\text{\# of patients in Maintenance mITT}}$$

The calculation will be done within treatment groups. Comparisons will only be made between the etrolizumab patients and placebo patients included in the mITT population.

**Null hypothesis H0:**  $\rho_{\text{Etro}} - \rho_{\text{PBO}} = 0$ ; the proportion of patients achieving remission at Week 62 among clinical responders at Week 10 in the placebo arm is the same as the proportion of patients achieving remission among clinical responders in the respective etrolizumab arm.

**Alternative hypothesis H1:**  $\rho_{\text{Etro}} - \rho_{\text{PBO}} \neq 0$ ; the proportion of patients achieving remission at Week 62 among clinical responders at Week 10 in the placebo arm is not the same as the proportion of patients achieving remission among clinical responders in the respective etrolizumab arm.

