#### **4.4.5 Supplementary Analyses**

To support the primary analyses the following supplementary analyses will be conducted;

- Proportion of patients in remission at Week 62 among clinical responders at Week 10 (including data collected whilst patients received rescue therapy)

- Proportion of patients in remission at Week 62 among clinical responders at Week 10 (using logistic regression model)
- Proportion of patients in remission at Week 62 among clinical responders at Week 10 (using clinical database derivation of clinical response at Week 10, if appropriate)

Definitions of clinical response are included in the project SAP, Section 4.4.2.1.4.

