**Table 3 Outcome Measures**

Outcome Measure	Definition
Mayo Clinic Score (MCS)	MCS (0–12) is a composite of 4 assessments, each rated from 0–3: stool frequency, rectal bleeding, endoscopy, and PGA
Partial Mayo Clinic Score (pMCS)	pMCS (0–9) is a composite of 3 assessments, each rated from 0–3: stool frequency, rectal bleeding, and PGA
Modified Mayo Clinic Score (mMCS)	mMCS (0–9) is a composite of 3 assessments, each rated from 0–3: stool frequency, rectal bleeding, and endoscopy
MCS Remission	MCS $\leq$ 2 with individual subscores $\leq$ 1 and a rectal bleeding subscore of 0
MCS Clinical Remission	MCS $\leq$ 2 with individual subscores $\leq$ 1
MCS Clinical Response	MCS with $\geq$ 3-point decrease and 30% reduction from baseline as well as $\geq$ 1-point decrease in rectal bleeding subscore or an absolute rectal bleeding score of 0 or 1
pMCS Remission	pMCS $\leq$ 2, with, rectal bleeding score of 0, PGA 0–1 and stool frequency subscore 0–1
mMCS Remission (excluding friability from ES=1)	mMCS $\leq$ 2, with, rectal bleeding score of 0, endoscopy 0–1 and stool frequency subscore 0–1 (Friability must be Absent for ES=1)
mMCS Remission (including friability in ES=1)	mMCS $\leq$ 2, with, rectal bleeding score of 0, endoscopy 0–1 and stool frequency subscore 0–1
pMCS Clinical Remission	pMCS $\leq$ 2, with, rectal bleeding score of 0–1, PGA 0–1 and stool frequency subscore 0–1
mMCS Clinical Remission (excluding friability from ES=1)	mMCS $\leq$ 2, with, rectal bleeding score of 0–1, endoscopy 0–1 and stool frequency subscore 0–1 (Friability must be Absent for ES=1)
mMCS Clinical Remission (including friability in ES=1)	mMCS $\leq$ 2, with, rectal bleeding score of 0–1, endoscopy 0–1 and stool frequency subscore 0–1
pMCS Clinical Response	A decrease in the pMCS of at least 2 points and at least 30% improvement from baseline, with an accompanying decrease in the rectal bleeding score by at least one point or an absolute rectal bleeding score of 0 or 1.
mMCS Clinical Response (excluding friability from ES=1)	A decrease in the mMCS of at least 2 points and at least 30% decrease (improvement) from baseline, with an accompanying decrease in the rectal bleeding score by at least one point or an absolute rectal bleeding score of 0 or 1. (Friability must be Absent for ES=1)

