#### **4.8 MISSING DATA**

The handling of intercurrent events explained in the individual studies will be applied before using the missing data handling approaches in this section. The handling of intercurrent events will occur in the order the intercurrent event occurs within the study.

To assess the robustness of the primary endpoint, a tipping point analysis will be conducted. The tipping point is defined as the difference in the number of missing events (i.e., remission) between the treatment groups that result in a change in the primary outcome conclusions (Yan et al. 2009). A two-dimensional plot will be produced for each primary comparison of etrolizumab (105 mg) vs. the comparator to evaluate where the tipping point lies.

The tipping point analysis will be used to assess the robustness of the primary endpoints within each study. The following groups of patients will always be considered nonremitters/non-responders within the tipping point analysis.

- Patients whose remitter/responder status can be calculated as a non-remitter/non-responder from their available sub scores, even when not all four MCS subscores are available.
- Patients who have received rescue therapy during the study.
- Patients who have discontinued study treatment early.

For all continuous endpoints, a MMRM model will be fitted to analyse UC-PRO domains assuming the data is missing at random. For missing SF/RB and IBDQ data single imputation worse observation carried forward (WOCF) post baseline will be applied to missing data, including when data is missing due to intercurrent event. An additional sensitivity analysis using observed case will be conducted, to assess the robustness of the analysis. All summary data will be reported using no imputation for missing data.

For any missing baseline data, no imputation of results data will be applied, and therefore, any endpoints requiring comparison back to baseline results will also be set to missing. To prevent a missing SF/RB subscore at baseline or post baseline which would lead to a missing MCS/mMCS/pMCS score, the anchor date used for selecting diary data to calculate RB/SF subscores can be imputed. If bowel prep date is missing, then endoscopy date can be used; if the endoscopy date is missing then the visit date can be used as the anchor date. If the PGA visit date is missing, the visit date will be imputed as Day 1+x weeks to allow RB and SF scores to be calculated.

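### The project SAP's stool-frequency formula drops the protocol's rounding; read literally, it can turn Week 62 remitters into failures and never the reverse

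*SAP*

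**What the plan says.** Protocol Appendix 4 gives the stool-frequency rule twice. For baseline, the value "will be calculated as the average (rounded to the nearest integer) from the three most recent stool frequency scores that were entered just prior" to bowel preparation. After baseline, "The post-baseline stool frequency value for endpoint assessment will be calculated as the average (rounded to the nearest integer").

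Project SAP section 4.4.2.1.1 gives the only formula for the subscore in the analysis plan: "Stool Frequency (SF) subscore= Average of 3 days daily diary scores". Table 2 of the project SAP says which diary days are selected, Table 3 gives the cut-points, section 4.8 covers missing data and anchor dates, and Appendix 3 illustrates day selection. None of them mentions rounding the stool-frequency average. Section 3.2 does state a rounding rule for another component: the endoscopy subscore is a median rounded up.

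For the primary endpoint, study SAP section 4.4.1.3 refers to project SAP section 4.4.2.1.4. Table 3 there defines remission as an MCS of at most 2, each subscore at most 1, "and a rectal bleeding subscore of 0".

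**The concern.** Daily scores are 0, 1, 2 or 3, so a three-day average is a multiple of one third. The remission cut-points are whole numbers. An average of 1.33 meets the subscore limit of 1 only if it is rounded, and an average of 0.33 can push a total of 2 over the limit if it is not. Whether such a patient is a Week 62 remitter therefore depends on which document the programmer follows.

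The same subscore enters every endpoint built on the full, modified or partial Mayo score. Section 4.8 makes the link explicit: "To prevent a missing SF/RB subscore at baseline or post baseline which would lead to a missing MCS/mMCS/pMCS score". It also enters:

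- the baseline summary and subgroup that split MCS at ≤9 and ≥10 (project SAP 4.3.2 and 4.4.3), where 9.33 or 9.67 fits neither category;
- the supplementary analysis in study SAP 4.4.5 "using clinical database derivation of clinical response at Week 10, if appropriate".

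No departure from the protocol is declared, although the study SAP declares others (sections 2.2 and 4.1.2.1).

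**Working it through.** **The plan's own figure.** Inputs from protocol 6.1 and study SAP 2.3.1: 105 per arm, two-sided 5% chi-squared test, difference 25 points, placebo remission 30% to 45%. The formula is power = Φ[(d − 1.96·SE₀)/SE₁], with SE₀ from the pooled rate and SE₁ from the separate rates. For 30% versus 55%:

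- SE₀ = √(2 × 0.425 × 0.575/105) = 0.0682
- SE₁ = √((0.30 × 0.70 + 0.55 × 0.45)/105) = 0.0660
- power = Φ[(0.25 − 0.1337)/0.0660] = Φ(1.76) = 96.1%

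By symmetry 45% versus 70% also gives 96.1%, and across the stated range the lowest value computed is 95.7% (placebo 37.5%). The claim of more than 90% is confirmed.

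**Effect on remission.** Take all 4³ = 64 diary triplets with rectal bleeding (RB), endoscopy (ES) and physician's global assessment (PGA) each 0 to 3, which makes 64 × 64 = 4,096 patterns. Classify each with stool frequency (SF) rounded and unrounded. With rounding, 100 patterns are remission; without it, 61. The 39 losses arise in two ways, both with RB 0:

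- **Diary sum 4**, for example 1, 1, 2: the average 1.33 rounds to 1, which is remission if ES + PGA ≤ 1. Unrounded, 1.33 exceeds 1. There are 12 such triplets and three ES/PGA pairs (0/0, 0/1, 1/0): 12 × 3 = 36.
- **Diary sum 1** (0, 0, 1 in any order) with ES 1 and PGA 1: rounded total 0 + 0 + 1 + 1 = 2, remission; unrounded total 2.33, failure. There are 3 triplets: 3.

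36 + 3 = 39 lost, 0 gained.

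**Why none is gained.** RB, ES, PGA and both cut-points are integers. If an unrounded SF satisfies SF ≤ 1 and SF ≤ 2 − ES − PGA, so does its ceiling, and the rounded value never exceeds the ceiling.

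**Related endpoints**, same count:

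| Endpoint | Remission with rounding | Lost without | Gained |
|---|---|---|---|
| MCS remission (primary) | 100 | 39 | 0 |
| MCS clinical remission | 140 | 57 | 0 |
| Modified-score remission | 64 | 24 | 0 |
| Partial-score remission | 64 | 24 | 0 |

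The one-way result does not extend to clinical response. With baseline SF 2 and other subscores totalling 9, and follow-up SF average 0.67 and others totalling 7, the rounded fall is 11 − 8 = 3. That is below 30% of 11, which is 3.3. The unrounded fall is 11 − 7.67 = 3.33, which meets it.

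**Illustration of power.** The documents give no loss rate. Assume both arms lose the same share of protocol-defined remitters:

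| Assumed loss | Placebo 30% | Placebo 45% |
|---|---|---|
| 0% | 96.1% | 96.1% |
| 5% | 94.5% | 93.8% |
| 10% | 92.4% | 90.9% |
| 15% | 89.9% | 87.4% |
| 20% | 87.0% | 83.3% |

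Power falls to exactly 90% at a loss of 14.9% (placebo 30%) or 11.4% (placebo 45%).

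**The case against.** The SAP is silent on rounding; it does not say the average is left unrounded. Its own text points to integers: four discrete stool-frequency categories, a subscore range of 0–1 in Table 3, and a split at ≤9 and ≥10 that leaves no room for fractions. Because the sponsor declares the departures it intends, an undeclared one suggests none was meant. All of this supports reading the gap as an omission, and that reading is accepted here.

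The pattern counts also need care. They weight every combination equally and treat PGA as free, although the scale anchors PGA 0 to subscores of 0. Of the 39 lost patterns, 24 pair PGA 0 with a rounded stool-frequency subscore of 1. Applying that anchor strictly leaves 40 remission patterns, of which 15 are still lost (12 with ES 0 and PGA 1, plus 3 with ES 1 and PGA 1), so the conclusion does not depend on the implausible cells. The loss rates in the power table are assumptions, and power stays at or above 90% until roughly one remitter in nine is lost.

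What does not stand is the idea that the protocol rule can be taken for granted. The SAP knowingly departs from protocol version 7 elsewhere and states rounding for endoscopy. A programmer following its one stool-frequency formula would produce a different primary numerator.

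**Conclusion.** The concern holds. The SAP formula, applied as written, conflicts with Protocol Appendix 4 and can only remove Week 62 remitters: 39 of 100 qualifying patterns, none in the other direction. The share of patients affected cannot be derived from the documents, and any loss of power depends on it.

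The limits are clear:

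- The primary denominator is fixed by randomisation and dosing: "Comparisons will only be made between the etrolizumab patients and placebo patients included in the mITT population".
- The strata for the primary test are also untouched: "The statistical analyses will be conducted using the stratification factors entered into the interactive voice/web based response system (IxRS) system at randomization".
- The same rule applies in both arms, so type I error is not inflated.
- The one-way statement covers the remission endpoints, not clinical response.

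This should be fixed, because the primary endpoint should not depend on which of two documents is consulted. Confidence is high on the conflict in the text and the direction of its effect. It does not extend to any particular effect on the trial's result.

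**What to change.** In project SAP section 4.4.2.1.1, and by reference in Table 2, define the stool-frequency subscore as the average of the three selected daily scores rounded to the nearest integer, at baseline and post-baseline, as in Protocol Appendix 4. State that this rounded value is used for the full, modified and partial Mayo scores. With three days no tie can occur, so no tie rule is needed.

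The cost is one phrase and a check that the derivation program rounds. The project SAP serves five studies, so the stool-frequency rule in the other protocols should be confirmed at the same time. If an unrounded average was in fact intended, it should be declared and justified as a departure from the protocol.
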